13.4 Quality Control and Quality Assurance

Novartis maintains a robust Quality Management System (QMS) that includes all activities involved in quality assurance and quality control, to ensure compliance with written Standard Operating Procedures as well as applicable global/local GCP regulations and ICH Guidelines.

Audits of investigator sites, vendors, and Novartis systems are performed by auditors, independent from those involved in conducting, monitoring or performing quality control of the clinical trial. The clinical audit process uses a knowledge/risk based approach.

Audits are conducted to assess GCP compliance with global and local regulatory requirements, protocols and internal SOPs, and are performed according to written Novartis processes.

14 Protocol adherence

This protocol defines the study objectives, the study procedures and the data to be collected on study participants. Additional assessments required to ensure safety of participants should be administered as deemed necessary on a case by case basis. Under no circumstances including incidental collection is an investigator allowed to collect additional data or conduct any additional procedures for any purpose involving any investigational drugs under the protocol, other than the purpose of the study. If despite this interdiction prohibition, data, information, observation would be incidentally collected, the investigator shall immediately disclose it to Novartis and not use it for any purpose other than the study, except for the appropriate monitoring on study participants.

Investigators ascertain they will apply due diligence to avoid protocol deviations. If an investigator feels a protocol deviation would improve the conduct of the study this must be considered a protocol amendment, and unless such an amendment is agreed upon by Novartis and approved by the IRB/IEC and Health Authorities, where required, it cannot be implemented.

16.1 Appendix 1: Clinically notable laboratory values and vital signs

Investigators are responsible for reviewing abnormal laboratory values for clinical significance, signing the laboratory reports to indicate their review, and reporting values considered clinically significant in the appropriate eCRF.

Any clinically significant abnormal laboratory value should be evaluated and followed-up by the investigator until normal or a cause for the abnormality is determined.

See [Appendix 2](#) for specific liver event and laboratory test trigger definitions and follow-up requirements.

See [Appendix 3](#) for specific renal alert criteria and actions.

Post-baseline vital signs will be flagged as notable abnormalities as follows:

1. Systolic/Diastolic blood pressure: $\geq 25\%$ decrease or $\geq 25\%$ increase from baseline
2. Pulse: ≥ 110 bpm with $\geq 15\%$ change from baseline, or < 50 bpm with $\geq 15\%$ change from baseline

16.2 Appendix 2: Suggested Liver event and laboratory trigger definitions & follow-up requirements

Table 16-1 Liver event and laboratory trigger definitions

	Definition/ threshold
Liver laboratory triggers If ALT, AST and total bilirubin normal at baseline:	
 ALT or AST > 5 × ULN ALP > 2 × ULN (in the absence of known bone pathology) Total bilirubin > 3 × ULN (in the absence of known Gilbert syndrome) ALT or AST > 3 × ULN and INR > 1.5 Potential Hy's Law cases (defined as ALT or AST > 3 × ULN and Total bilirubin > 2 × ULN [mainly conjugated fraction] without notable increase in ALP to > 2 × ULN) Any clinical event of jaundice (or equivalent term) ALT or AST > 3 × ULN accompanied by (general) malaise, fatigue, abdominal pain, nausea, or vomiting, or rash with eosinophilia Any adverse event potentially indicative of a liver toxicity*
If ALT or AST abnormal at baseline:	
 ALT or AST > 2x baseline or > 300 U/L (whichever occurs first)

*These events cover the following: hepatic failure, fibrosis and cirrhosis, and other liver damage-related conditions; non-infectious hepatitis; benign, malignant and unspecified liver neoplasms ALP: Alkaline phosphatase, ALT: Alanine aminotransferase, AST: Aspartate aminotransferase, ULN: upper limit of normal
	

Table 16-2 Follow up requirements for liver laboratory triggers with liver symptoms

	ALT	TBL	Liver Symptoms	Action
ALT increase without bilirubin increase:				
	
If normal at baseline: ALT > 3 x ULN
 
If elevated at baseline: ALT > 2 x baseline or > 300 U/L (whichever occurs first)
	Normal For participants with Gilbert's syndrome: No change in baseline TBL	None	
 No change to study treatment Measure ALT, AST, ALP, GGT, TBIL, INR, albumin, CK, and GLDH in 48-72 hours. Follow-up for symptoms.
	
If normal at baseline: ALT > 5 x ULN for more than two weeks
	Normal For participants with Gilbert's syndrome: No	None	
 Interrupt study drug Measure ALT, AST, ALP, GGT, TBIL, INR,

	ALT	TBL	Liver Symptoms	Action	
	If elevated at baseline: ALT > 3 x baseline and >10 x ULN	change in baseline TBL		albumin, CK, and GLDH in 48-72 hours. 
 Follow-up for symptoms. Initiate close monitoring and workup for competing etiologies. Study drug can be restarted only if another etiology is identified and liver enzymes return to baseline. 	
	If normal at baseline: ALT > 8 x ULN	Normal	None		
ALT increase with bilirubin increase:					
	If normal at baseline: ALT > 3 x ULN If elevated at baseline: ALT > 2 x baseline	TBL > 2 x ULN For participants with Gilbert's syndrome: Doubling of direct bilirubin	None		
	If normal at baseline: ALT > 3 x ULN If elevated at baseline: ALT > 2 x baseline	Normal or elevated	Severe fatigue, nausea, vomiting, right upper quadrant pain		

Table 16-3 Follow up requirements for liver laboratory triggers

Criteria	Actions required	Follow-up monitoring
Total Bilirubin (isolated)		
>1.5 – 3.0 ULN	
 Maintain treatment Repeat LFTs within 48-72 hours 	Monitor LFTs weekly until resolution ^a to ≤ Grade 1 or to baseline
> 3 - 10 × ULN (in the absence of known Gilbert syndrome)	
 Interrupt treatment Repeat LFT within 48-72 hours Establish causality Record the AE and contributing factors (e.g. conmeds, med hx, lab) in the appropriate CRF 	Monitor LFTs weekly until resolution ^a to ≤ Grade 1 or to baseline (ALT, AST, total bilirubin, Alb, PT/INR, ALP and GGT) Test for hemolysis (e.g. reticulocytes, haptoglobin, unconjugated [indirect] bilirubin)
> 10 x ULN	
 Discontinue the study treatment immediately Establish causality Record the AE and contributing factors(e.g. conmeds, med hx, lab)in the appropriate CRF 	ALT, AST, total bilirubin, Alb, PT/INR, ALP and GGT until resolution ^a (frequency at investigator discretion)

Criteria	Actions required	Follow-up monitoring
General symptoms		
Any AE potentially indicative of a liver toxicity*	
 • Consider study treatment interruption or discontinuation • Establish causality • Record the AE and contributing factors(e.g., conmeds, med hx, lab)in the appropriate CRF 	Investigator discretion

^aResolution is defined as an outcome of one of the following: (1) return to baseline values, (2) stable values at three subsequent monitoring visits at least 2 weeks apart, (3) remain at elevated level after a maximum of 6 months, (4) liver transplantation, and (5) death.
 
*(General) malaise, fatigue, abdominal pain, nausea, or vomiting, or rash with eosinophilia
		

Based on investigator's discretion investigation(s) for contributing factors for the liver event can include: Serology tests, imaging and pathology assessments, hepatologist's consultancy; obtaining more detailed history of symptoms and prior or concurrent diseases, history of concomitant drug use, exclusion of underlying liver disease.

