6.1.3 Treatment duration

The total treatment duration of hydroxychloroquine is 10 days. The approach to include a loading dose on Day 1 is preferred in order to rapidly reach higher target tissue drug concentrations. The total treatment duration of azithromycin will be 5 days.

In case a participant is discharged prior to Day 10, they may complete study treatment as planned, at home, until Day 10 if QTcF \leq 480 ms at the time of discharge based on the local ECG data. Otherwise, treatment will be discontinued at the time of discharge.

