8.1 Screening

Screening

The screening period will be a maximum of 4 days, and is used to check the participant's eligibility after obtaining informed consent and prior to the randomization on Day 1. The assessments required at screening are summarized in [Table 8-1](#). If all eligibility criteria are confirmed screening and randomization may occur on the same day.

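### Table 16-2 drops its interrupt instruction at ALT above 8 x ULN when bilirubin is mildly raised, or raised but unchanged in Gilbert's syndrome (no symptoms, normal ALT at entry)

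*Protocol*

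**What the plan says.** Protocol Appendix 2, Table 16-2 has five rows, numbered here in printed order. Where a row has a separate criterion for elevated entry ALT, it is given only if it matters.

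- Row 1: ALT above 3 x ULN, bilirubin normal (or, in Gilbert's syndrome, unchanged from baseline), no symptoms. Treatment continues; a laboratory panel is repeated in 48 to 72 hours.
- Row 2: "If normal at baseline: ALT > 5 x ULN for more than two weeks", or "If elevated at baseline: ALT > 3 x baseline and >10 x ULN". The bilirubin and symptom conditions are those of row 1. The drug is interrupted, the panel repeated, and close monitoring and a search for other causes begun.
- Row 3: "If normal at baseline: ALT > 8 x ULN", bilirubin normal, no symptoms. There is no Gilbert's wording. The action cell is blank in the extracted text.
- Row 4: ALT above 3 x ULN, no symptoms. The bilirubin cell opens "TBL > 2 x ULN For participants with" Gilbert's syndrome and then asks for a doubling of direct bilirubin.
- Row 5: ALT above 3 x ULN with listed symptoms, at normal or elevated bilirubin.

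Rows 1 to 3 stand under a heading for ALT rises without a bilirubin rise.

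Section 10.2.2 suggests following up every Table 16-1 liver event: repeat chemistry and, if the rise is confirmed, close observation with interruption to be considered, discontinuation if appropriate, and causality assessment. It points to Table 16-2 for the detailed actions. The end of section 10.2.1 puts local practice first and calls the liver guidance suggested. Section 9.1.1 requires the investigator to stop treatment believed to be harming the participant.

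On timing, section 6.1.3 states "The total treatment duration of hydroxychloroquine is 10 days" and section 8.1 states "The screening period will be a maximum of 4 days". Table 8-1 places screening on Days -3 to 0 and the end of study on Day 40.

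**The concern.** A safety table should not become less cautious as the liver picture worsens. At ALT above 8 x ULN, Table 16-2 gives an interrupt instruction when bilirubin is normal, none when it is above 1 and up to 2 x ULN, and the instruction again above 2 x ULN. In Gilbert's syndrome with raised but stable bilirubin, the only matching row tells the site to carry on dosing. That is a written rule pointing the wrong way, which is more than a missing detail.

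Also, row 2's criterion of more than two weeks sits in a table for a drug given for 10 days, so its interrupt action looks out of place. What is at stake is the clarity of instructions to sites. No efficacy result, safety count or power figure uses this table.

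**Working it through.** **Reading used.** Row 3, and rows 4 and 5 below it, are taken to share row 2's interrupt action, because they carry no other action text. Normal bilirubin is taken as at or below 1 x ULN. Row 5 allows normal or elevated bilirubin, so the table itself separates the two terms.

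**Step 1: no symptoms, normal entry ALT, no Gilbert's syndrome, 6 days above 5 x ULN.** Values are multiples of ULN.

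| ALT | Bilirubin 0.9 | 1.5 | 2.0 | 2.1 |
|---|---|---|---|---|
| 4, 6, 7.9 | row 1: no change | no row | no row | row 4: interrupt |
| 9, 20 | rows 1 and 3: interrupt, if the more severe applies | no row | no row | row 4: interrupt |

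At ALT 9 and bilirubin 0.9, rows 1 and 3 both match and give opposite instructions. The table states no order of precedence.

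**Step 2: Gilbert's syndrome, bilirubin unchanged at 1.5, 2.0 or 2.1, direct bilirubin not doubled.** Row 3 fails because bilirubin is not normal and the row has no Gilbert's wording. Row 4 fails because direct bilirubin has not doubled. Row 1 is met. All 5 ALT values x 3 bilirubin values = 15 cells therefore read no change to treatment, even at ALT 20.

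**Step 3: does other text restore the instruction?** Table 16-3's bilirubin rows are for isolated bilirubin rises. Its last row says only "Consider study treatment interruption or discontinuation". Section 10.2.2 leaves interruption and discontinuation to discretion.

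**Step 4: row 3 applied at any bilirubin, most severe row taken.** In step 1, 2 ALT values x 2 bilirubin values = 4 of 20 cells move from no row to interrupt. The other 16 are unchanged, including all 3 x 4 = 12 cells with ALT 4 to 7.9. In step 2, 2 x 3 = 6 of 15 cells move from no change to interrupt. No cell becomes less cautious.

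**Step 5: the two-week criterion.**

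- Longest span from the first screening day to the last dosing day: 10 - (-3) = 13 days, below 14.
- First day with more than 14 days elapsed = onset day + 15.
- Onset Day 1: Day 16, which is 16 - 10 = 6 days after the last dose and 40 - 16 = 24 days before Day 40.
- Onset Day 4, the first scheduled chemistry after baseline: Day 19, which is 9 days after the last dose and 21 days before Day 40.

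The interrupt action therefore cannot operate. The repeat panel, close monitoring and search for other causes can, because participants are followed to Day 40.

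**The case against.** The strongest reply is that little turns on this table. The appendix is labelled suggested, local practice governs, and listed severe symptoms lead to row 5 at any bilirubin. ALT above 5 x ULN remains a Table 16-1 event when entry ALT, AST and bilirubin are normal. Section 10.2.2 then calls for repeat chemistry and close observation and allows discontinuation, and section 9.1.1 obliges the investigator to stop harmful treatment. All of this stands and limits the severity. It does not put the missing instruction back. The Table 16-1 trigger is also conditioned on normal bilirubin at entry, which a participant with Gilbert's syndrome may not have.

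A second reply is that the fix is selective. That is fair. ALT above 3 and up to 8 x ULN with bilirubin above 1 and up to 2 x ULN still has no row. Row 2's criterion for elevated entry ALT also requires normal bilirubin, although it includes the Gilbert's wording. This point is confined to normal entry ALT above 8 x ULN; whether to go further is a clinical choice for the sponsor.

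A reader might infer that the two-week criterion is dead text to be deleted. The documents do not support that. For ALT held at 6 x ULN for more than two weeks, with normal bilirubin and no symptoms, it is the text that prompts close monitoring and a search for other causes. Deleting it would leave only row 1. The grid in step 1 does not test deletion, because at 6 days the criterion is inactive in every cell.

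A reader might also infer that Day 4 is everyone's only scheduled chemistry between baseline and the last dosing day. Participants discharged before Day 10 have the Day 10 assessments, including chemistry, before discharge (section 8.5.2) and may continue dosing at home.

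**Conclusion.** The point holds as a minor, optional correction. For a participant without symptoms and with normal entry ALT, Table 16-2 gives no row at ALT above 8 x ULN with bilirubin above 1 and up to 2 x ULN. In Gilbert's syndrome, with raised, unchanged bilirubin and direct bilirubin not doubled, it gives only the row that leaves treatment unchanged. The interrupt action of the two-week criterion cannot operate during a 10-day course, but its other actions can.

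It would be too strong to say that such participants go unmonitored: sections 10.2.2 and 9.1.1 and local practice remain. The conclusion depends on reading row 3's blank action cell as merged with row 2's, which is the natural reading but cannot be confirmed from the extracted text. The documents give no basis for estimating how many participants would fall in the gap. The SAP records that the study was halted with 20 participants randomized, so the practical value lies mainly in any reuse of the table.

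**What to change.** In Table 16-2:

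1. In the row for ALT above 8 x ULN, replace the normal-bilirubin condition with any bilirubin value, including Gilbert's syndrome. Give the row its own heading, since it would no longer belong under ALT rises without a bilirubin rise.
2. State that where several rows are met, the most severe applies.
3. Keep the two-week criterion and add a note that, with 10 days of dosing, it governs post-dosing monitoring only. Leave the elevated-entry-ALT criterion in that row as it is.

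The text cost is one cell, one heading, one sentence and one note, with no new scheduled visit. The clinical cost is an occasional extra interruption at ALT above 8 x ULN with mildly raised bilirubin or Gilbert's syndrome, together with a search for other causes. Where no row applied before, the 48 to 72 hour panel also adds INR, albumin, CK and GLDH to the repeat chemistry of section 10.2.2; in Gilbert's syndrome row 1 already asks for that panel. Because restart requires another cause to be identified and enzymes back at baseline, an interruption may in practice end a 10-day course.

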16.3 Appendix 3: Suggested Specific Renal Alert Criteria and Actions and Event Follow-up

Table 16-4 Specific Renal Alert Criteria and Actions

Serum Event	
Serum creatinine increase 25 - 49% compared to baseline	Confirm 25% increase after 24-48h Follow up within 2-5 days
Acute kidney injury: serum creatinine increase $\geq 50\%$ compared to baseline	Follow up within 24 -48h if possible Evaluate the need for study treatment interruption or discontinuation Consider specialized treatment
Urine Event	
New dipstick proteinuria $\geq 1+$ Albumin- or Protein-creatinine ratio increase ≥ 2 -fold Albumin-creatinine ratio (ACR) ≥ 30 mg/g or ≥ 3 mg/mmol; Protein-creatinine ratio (PCR) ≥ 150 mg/g or ≥ 15 mg/mmol	Confirm value after 24-48h Perform urine microscopy Evaluate the need for study treatment interruption / or discontinuation
New dipstick glycosuria $\geq 1+$ not due to diabetes	Blood glucose (fasting) Perform serum creatinine, ACR
New dipstick hematuria $\geq 1+$ not due to trauma	Urine sediment microscopy Perform serum creatinine, ACR
For all renal events:	
Document contributing factors in the CRF: co-medication, other co-morbid conditions, and additional diagnostic procedures performed Monitor subject regularly (frequency at investigator's discretion) until either: Event resolution: sCr within 10% of baseline or protein-creatinine ratio within 50% of baseline, or Event stabilization: sCr level with $\pm 10\%$ variability over last 6 months or protein-creatinine ratio stabilization at a new level with $\pm 50\%$ variability over last 6 months.

Table 3-1	Sensitivity of sample size to different response rates for 148 participants per group (N=444) and treatment differences for level of significance $\alpha = 0.05$	24
Table 5-1	CTCAE grades for laboratory parameters (CTCAE Version 5.0)	25
Table 5-2	Participant classification	27
Table 5-3	Type of pulmonary/Ventilatory support.....	28
Table 5-4	9-point ordinal scale for clinical status	28

List of figures

Figure 1-1	Study design	9
------------	--------------------	---

List of abbreviations

AE	Adverse event
ATC	Anatomical Therapeutic Classification
AUC	Area Under the Curve
bid	bis in diem/twice a day
CSR	Clinical Study report
CRS	Compound Case Retrieval Strategy
CTC	Common Toxicity Criteria
CTCAE	Common Terminology Criteria for Adverse Events
DMC	Data Monitoring Committee
FAS	Full Analysis Set
FPFV	First participant first visit
eCRF	Electronic Case Report Form
hs-CRP	high-sensitivity C-reactive Protein
IVR	Interactive Voice Response
IRT	Interactive Response Technology
IWR	Interactive Web Response
LFT	Liver function test
MedDRA	Medical Dictionary for Drug Regulatory Affairs
NMQs	Novartis MedDRA queries
o.d.	Once Daily
LLOQ	Lower Limit of Quantification
PCR	Polymerase Chain reaction
PFS	Progression-Free Survival
PK	Pharmacokinetics
PPS	Per-Protocol Set
PRO	Patient-reported Outcomes
PT	Preferred term
qd	Qua'que di'e / once a day
QoL	Quality of Life
RAP	Report and Analysis Process
RAS	Randomized Analysis Set
SAF	Safety Analysis Set
SAP	Statistical Analysis Plan
SARS-CoV	severe acute respiratory syndrome coronavirus
SMQ	Standardized MedDRA Query
SOC	System Organ Class
SoC	Standard of Care
SpO2	Supplemental Oxygen
TFLs	Tables, Figures, Listings
WHO	World Health Organization

1 Introduction

The purpose of the Statistical Analysis Plan (SAP) is to describe the implementation of statistical analysis planned in the clinical study protocol. The clinical study report (CSR) of the JWT629A12301 study will be produced from this SAP.

On the 19th of June, 2020 a decision was made to halt the JWT629A12301 study for feasibility reasons. Hence only an abbreviated CSR will be created for this study. Analysis covered in the original SAP were reduced and/or simplified accordingly

The content of this SAP is based on the original clinical trial protocol of the JWT629A12301 study (Release date: 08-APR-2020).

1.1 Study design

This study is a multi-center, randomized, double-blind, three-arm parallel-group, placebo-controlled trial to evaluate the safety and efficacy of hydroxychloroquine monotherapy or in combination with azithromycin in participants with moderate and severe COVID-19 disease. The study will include: a screening period of up to four days to obtain the informed consent and assess participant's eligibility; a treatment period of 10 days; and an observation period of an additional 30 days (until Day 40) with Day 40 being the end of study visit. All participants are expected to be treated with available standard of care (SoC) therapy for COVID-19 disease throughout the study ([Figure 1-1](#)).

Approximately 444 participants were to be randomized into either of three arms with a 1:1:1 ratio. When the decision was made to halt the study, a total of 20 participants had been randomized (including one mis-randomized participant).

[figure not shown]
Study will be conducted in the United States.

No formal interim analysis is planned for this trial.

The CSR will be finalized after the final database lock, once the 20 randomized participants have completed Day 40 or discontinued study prior to Day 40.

Considering the limited number of participants randomized, only serious adverse events were reviewed during safety monitoring using a data monitoring committee (DMC).

Figure 1-1 Study design

All participants will be treated with the best available standard of care for COVID-19 disease throughout the study

¹ The total treatment duration of hydroxychloroquine will be 10 days. The total treatment duration of azithromycin will be 5 days. In case a participant is discharged before the end of treatment period (Day 10) he/she may continue study medication at home until Day 10 if QTcF \leq 480 ms at the time of discharge based on the local ECG data. Otherwise, treatment will be discontinued at the time of discharge (before Day 10).

² The loading dose of AZI/matching placebo (Day 1) should be taken 4 hours after loading dose of HCQ/matching placebo

³ After HCQ/matching placebo loading dose on Day 1, the following HCQ/matching placebo doses as a maintenance therapy should be initiated within approximately 8 hours (not to exceed 12 hours).

HCQ: hydroxychloroquine, AZI: azithromycin, o.d.: once a day, t.i.d: three times a day

